3.6 DATA SOURCES

3.6.A QUESTIONNAIRES

Questionnaires will be administered at baseline, 1-, 2-, 4-, 6-, 7-, 8-, and 12-week study visits. At weeks 4 and 8, assessments of medication tolerability, discontinuation, treatment side effects, self-reported adherence, and self-reported pain (BPI) will occur. At week 12 (post-treatment), there will be an assessment of self-reported pain (BPI) only. At weeks 1, 2, 6, and 7 brief assessment of tolerability, side effects, and adherence will occur.

3.6.B. URINE

A pregnancy test will be administered by trained clinical research staff at screening to determine eligibility and at each study visit (except for 8- and 12-weeks).

Pregnant women will be excluded from the study due to some reports suggesting possible adverse events with study medications. Participants found to be pregnant will discontinue their study medication but will still be followed-up for the duration of the study.

Urine will also be checked at screening and baseline, as part of the naloxone challenge, to ensure that participants have not recently used opiates (as opioid receptor antagonists would be contraindicated as they could precipitate withdrawal). The urine drug test will test for a range of opioids, specifically opiates (products of the poppy plant – morphine, heroin) and synthetic opioids (specifically methadone). If new opioids appear on the scene in Russia, such as fentanyl, then we will begin testing for this, but currently that is not thought to be an issue.

3.6.C. BLOOD

Blood will be collected at screening and the 4- week study visit to assess AST/ALT and/or Creatinine levels. Blood may also be collected at the 6-week study visit for liver function testing, if indicated at the participant's 4-week study visit (see Section 3.4E).

Additional blood will be collected at baseline and the 8-week study visit to assess pro-inflammatory biomarkers, IL-6 IL-1 β , IL-10, and TNF-alpha, as well as measures of HIV control, CD4 cell count and HIV viral load. Levels of these pro-inflammatory markers will be measured on blood samples collected using commercially available enzyme-linked immunosorbent assay kits (R&D Systems). Blood specimens will be processed and analyzed locally at the ImmunoBioService (IBS) under the direction of [name]. Per current Russia ARCH protocols, the local laboratory will collaborate with study consultant [name] who directs the Laboratory for Clinical Biochemistry Research (LCBR) at the University of Vermont, which specializes in biomarker testing in large population studies and clinical trials.

Test	Timepoint
Red Tube (9 mL)	
IL-6	Baseline, 8-weeks
IL-10	Baseline, 8-weeks
IL-1β	Baseline, 8-weeks
TNF-α	Baseline, 8-Weeks
Purple EDTA (4 mL)	
HIV RNA	Baseline, 8-Weeks
Green Top (4 mL)	
CD4	Baseline, 8-Weeks
Red Top (4 mL)	
AST/ALT	Screening, 4-weeks, 6- weeks (if indicated)
eGFR (creatinine)	Screening

Unsuccessful Draw Protocol

At baseline and 8-weeks, a blood draw will be considered successful if the EDTA purple top tube is at least half full, the green top tube is at least \(^34\) full, and the red top tube is full.

Participants with unsuccessful baseline blood draws will receive 1/3 (350 RUB) compensation at the initial attempt, 1/3 (333 RUB) at their second attempt, and the final 1/3 (350 RUB) at their third attempt. If the second attempt is successful, they will receive the remaining 2/3 (650 RUB) of the compensation at that time.

If the blood draw is unsuccessful at the 8-week study visit, the participant will be given partial (1/2, 750 RUB) compensation for completion of the assessment. The participant has 30 days to complete the blood draw attempt. Blood draw attempts will occur weekly (up to 4 times, the fourth attempt will correspond with the participant's 12-week study visit). The remaining 1/2 (750 RUB) of the compensation will be divided between the 4 weekly attempts (187 RUB for each attempt). If the second or third attempts are successful, participants will receive the remaining 1/2 or 3/4 (375 RUB-561 RUB) at that time.

		Blood draw to take place prior to assessment; If blood draw is not
	Timing of	successful, no assessment is
	blood draw	conducted.
Baseline		If blood draw is not successful,
Daseille		participant receives partial (1/3)
	Compensation	compensation.
	Window	30 days after completion of screener
		3 weekly attempts; at final attempt
	Final attempt	provide full compensation.
Timing of		If blood draw is not successful,
	blood draw	proceed to assessment.
Follow up*		Given partial (1/2) compensation
(8-week visit	Compensation	for completion of assessment.
only)		30 days after completion of
Office	Window	assessment.
		4 weekly attempts; at final attempt
	Final attempt	provide full compensation.

3.6.D. COLD-PRESSOR TESTING

The cold-pressor test (CPT) is an experimental model that assesses cold pain threshold and tolerance. It is a research paradigm that has been used by researchers for decades, and has been utilized to measure enhanced sensitivity to cold pain (hyperalgesia). The investigators will use an automatic cooling water bath that keeps a constant temperature of 0–2 degrees Celsius. Participants are instructed to place their dominant arm in the cold water bath so that ice water covers the hand and approximately 10 cm of the forearm, to verbally indicate when they first perceive pain and, to rate their pain on a scale of 0-100 at its very worse, and when they can no longer tolerate the ice bath, to remove their arm from the water. The time from submersion to those events will be measured using a stopwatch. Cold pain threshold is measured as number of seconds to the initial perception of pain, and cold pain tolerance is measured as seconds until withdrawal of hand. Trials will be discontinued at 3 minutes since after this time pain severity diminishes as numbness sets in. This data will be collected at baseline, week 4, week 8, and week 12. Participants will be requested to refrain from over the counter analgesic use (non-steroidal anti-inflammatory pain medications or acetaminophen) for 24 hours prior to the study visit.

3.6.E. DAILY PAIN DIARY

Participants will be asked to keep a daily written record ("daily diary") of pain severity, medication adherence, and alcohol use.

4. STUDY PROCEDURES

4.1 RECRUITMENT

Former Russia ARCH, St PETER, LINC-II and PETER PAIN participants, who have agreed to be contacted for future studies, will be screened for the study. Current St PETER participants will also be screened for the study at their final St PETER study visit. Recruitment beyond these study populations will occur at local NGOs and Russia ARCH network hospitals including the major clinical HIV hospitals (Botkin Infectious Disease Hospital, Leningrad Regional AIDS Center, St. Petersburg City AIDS Center) and addiction hospitals (Leningrad Regional Center for Addictions, St. Petersburg City Addiction Hospital) through notification of patients and providers at these sites. At each of the recruitment sites flyers with information about the trial will be distributed to clinicians and peers working with HIV-positive patients. Flyers will provide a phone number (at Pavlov) for interested individuals to call to find out more about the study and undergo initial screening over the phone. On occasion, Pavlov research assessors may travel to screen participants at the affiliated clinical locations. Flyers will also be posted on social media platforms through the Pavlov University social media accounts/pages.


If a participant is screened over the phone, the participant will be re-screened in-person.

If a participant is not eligible during the phone screening or in-person screening, research assessors can re-contact the potential participant in the future to be re-screened. The decision to re-screen will be based on the cause of their ineligibility (i.e. HIV-negative individuals will not be re-contacted) and the likelihood that their eligibility will change (i.e. those who do not present a normal creatinine level at the first re-screening will not be re-contacted as kidney function will be unlikely to change). Decisions for rescreening will be clinically decided.

Participants' screening IDs will be linked to their subject ID in a separate REDCap project. Contact information will also be collected on this REDCap project. Study data will be collected on REDCap and organized by either screening ID or study ID.

4.3 INFORMED CONSENT

Research assessors will conduct the consent process as well as obtain written consent. After eligibility and interest in enrollment is determined, an RA will administer and document the informed consent of the participant in a private location. The study will be explained to eligible participants who will be offered participation in the study. Research assessors will answer any questions the participants may have including risks, benefits and alternatives (including non-participation) to participation, and will provide written materials describing the study. If participants are unsure whether they would like to participate, they will be allowed any amount of time they need to consider participation in the study. If the participant is not able to make a decision on the day of the initial visit, s/he will be invited to contact the study team once they have made their decision, at which point s/he will be re-screened, if more than 3 days have passed since his/her initial screening. The written informed consent (in Russian), including the risks, benefits and alternatives, will be signed by the participant and the research assessor. As part of the informed consent process we will make it explicit to participants that their involvement in the study does not constitute medical treatment and that they will not receive any HIV medical care as part of the study. We will provide a handout with information on addiction and HIV treatment services to participants at the baseline visit. A copy of the informed consent will be provided to the participant and a copy will be maintained by the research team. The time the administration of the informed consent began, and the time the informed consent form was dated and signed by the participant will be captured in the study website. Potential participants will be informed that refusal to participate will not affect their medical care at PSMU in any way and they will be informed of their right to drop out of the study at any time.

4.4 VISIT FLOW

Pre-screen (optional):

• Screening questions administered over the phone

Screening visit:

- Screening Questions
- Informed Consent and Enrollment

- Conduct HIV, urine drug test, draw blood for AST/ALT and Creatinine testing (if recent test result not provided), and pregnancy testing
- Compensate participant, collect locator/contact information and check contact phone numbers
- Schedule return visit, if eligible
- Provide resource document, appointment reminder card

Baseline visit:

- Review and update locator/contact information, verifying new numbers, as necessary
- Conduct urine drug testing and pregnancy testing
- Administer naloxone challenge
- Administer assessment questionnaire
- Assess baseline symptoms
- Randomize participant
- Conduct cold-pressor test
- Draw blood for biomarker, CD4, and HVL testing
- Introduce study medication and instructions and develop an adherence plan
- Provide study medication
- Observe participant for 30 minutes after the participant takes the first dose
- Compensate participant; provide appointment reminder card, participation card, daily diary, and schedule next visit

1-, 2-, 6-, and 7-week medication visit:

- Review and update locator/contact information, verifying new numbers, as necessary
- Collect a urine sample to check for pregnancy (females only)
- Draw blood for ALT/AST testing, if indicated (6-week only)
- Administer a brief assessment of tolerability and side effects
- Assess medication adherence
- Provide study medication (1-week, 2-week, 4-week, 6-week visits)
- Compensate participant and schedule next visit

4-, 8-, and 12-week full study visit:

- Review and update locator/contact information, verifying new numbers, as necessary
- Collect a urine sample to check for pregnancy (4-week only, females only)
- Assess medication adherence
- Administer assessment questionnaire
- Conduct cold-pressor test
- Draw blood for ALT/AST (4-week, and 6-week if indicated only) and biomarker, CD4, and HVL (8-week only) testing
- Provide study medication (4-week only)
- Compensate participant and schedule next visit (4- and 8-week only)

4.5 QUALITY ASSURANCE

Informed consent quality assurance

The RA will review Informed Consent Forms (ICFs) for completeness with the participant present. Items to check will include, but are not limited to: responses/initials collected for all questions, correct version of ICF used, signed and dated by both subject and RA. Both the RA and project manager will review ICFs weekly for completeness.

Assessment quality assurance

During the assessment, if the participant provides conflicting answers or answers that did not make logical sense (either within the same section or between sections), the RA will gently try to help the participant arrive at more logical answers. However, the RA will not force the participant to change his or her answers. Certain quality assurance checks are built into the assessment. The system will flag any inappropriate responses and prevent the RA from continuing until the issue is resolved. The RA will never guess to correct a mistake. The only instance when a change can be made to the completed assessment is in the event that the RA is 100% certain that an error was made in data entry.

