2.2 STUDY OUTCOMES

Primary Outcomes: The primary outcome for this study is change in past week pain severity and pain interference (score 0-10) from baseline to week 8. Pain severity and interference will be measured using the Brief Pain Inventory (BPI).

Secondary Outcomes:

Changes in the following secondary outcomes between baseline and week 8 will also be compared among the 3 arms:

- 1) Biomarkers IL-6, IL- β , 1L-10, and TNF- α . Levels of these pro-inflammatory markers will be measured on blood samples collected using commercially available enzyme-linked immunosorbent assay kits (R&D Systems).
- 2) Cold pain tolerance. This will be measured using the cold-pressor test; briefly it is the number of seconds a participant can keep hand submerged in cold water bath.

[figure not shown]
- 3) Percentage of past month heavy drinking days. We will use the Timeline Follow Back to assess drinks per day in the past 30 days. Using a calendar, people provide retrospective estimates of their daily drinking over the past 30 days from the interview date. Definitions of heavy drinking are based on NIAAA guidelines for at-risk drinking (i.e., drinking greater than 14 standard drinks per week/greater than 4 drinks in a day for men; greater than 7 drinks in the past week/greater than 3 drinks in a day for women).
- 4) Measures of HIV control: CD4 cell count and HIV viral load will be measured on participants.

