6.2 THE METHODS AND TIME FOR ASSESSING, RECORDING, AND ANALYZING SAFETY PARAMETERS

- Participant symptoms will be assessed at baseline to document any chronic conditions or symptoms that existed prior to introduction of study medication. These will be documented on the Baseline AE log. This list will be reviewed and compared to reported events throughout the study. If the participant reports the same ongoing symptom (same severity) during subsequent visits, the symptom should not be recorded as an Adverse Event (AE). If the event is new (not previously reported) or worsened, as determined by RA, then the AE should be reported.
- During each scheduled visit, the RA will ask the participant how he or she feels and review the list of symptoms of concern (starting with the symptoms recorded at the previous visit). Any event that meets the above criteria for an AE/SAE/UP must be recorded. In the case of unresolved AEs, clinical staff will update the AE log with any follow-up information that is gathered during their investigation.
- The site will receive the results of all blood work that is performed on study participants from the designated lab. If the lab results meet the criteria described in the protocol as an AE and are considered clinically significant by the site clinician then an AE will be recorded. **See**"Discontinuation of Medications" for severe hepatoxicity thresholds.
 - O Participants will be alerted of abnormal lab results and will receive a recommendation to see their local provider. All abnormal lab results obtained at the baseline visit will be listed on the Baseline AE log.

- All AEs will be assessed to determine if they meet criteria for a Serious Adverse Event (SAE). [name], MA, MPH and [name], MPH will be designated to distinguish a serious adverse event (SAE) from a non-serious adverse event. Drs. [name], PhD, D.Med Sci and [name]. PhD will monitor SAE and AE on site. If the AE is serious, then the SAE form must be completed and appropriate reporting measures followed (see below). Investigators are encouraged to consult with the US team, if they are uncertain how to classify an event.
- The list of subject's current medications will be reviewed and updated at every study visit, starting at baseline.

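### The rule in section 4.5 that assessors help participants toward more logical answers does not exempt the self-reported Brief Pain Inventory, so assessor judgement can enter the primary outcome; a neutral re-read rule would close the gap cheaply.

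*Combined protocol and SAP*

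**What the plan says.** Section 4.5, under assessment quality assurance, sets one rule for the whole interview. It is triggered "if the participant provides conflicting answers or answers that did not make logical sense (either within the same section or between sections"), and then "the RA will gently try to help the participant arrive at more logical answers".

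The paragraph also sets limits. It says that "the RA will not force the participant to change his or her answers" and "The RA will never guess to correct a mistake". It adds: "The only instance when a change can be made to the completed assessment is in the event that the RA is 100% certain" of a data-entry error. On the electronic form, "The system will flag any inappropriate responses and prevent the RA from continuing until the issue is resolved".

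The BPI falls inside this rule. Section 2.2 makes the baseline-to-week-8 change in BPI severity and interference the primary outcome. Section 3.6.A calls the BPI self-reported, section 5.1 lists it among the interview instruments, and section 7.3 has research assessors enter assessment data directly. No section exempts the BPI, gives a neutral script for the prompt, or asks that the first answer be kept.

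**The concern.** A date or a medication name can be checked for logic because there is a fact behind it. A pain rating has no outside standard: the participant's own number is the measurement. An instruction to move answers toward consistency, applied to such items, lets the assessor's idea of what fits influence the rating. The between-sections trigger matters most. The BPI is collected alongside mood, anxiety, quality-of-life and symptom questions (table in section 5.2), so a rating could be queried because it sits oddly with another scale.

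Section 2.7.A says that the pilot exists mainly to estimate effects for a later trial. At stake are the estimated differences, their standard deviation, and the separation between severity and interference, which section 8.1 treats together as the primary outcome.

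**Working it through.** **1. Do the limits in section 4.5 prevent leading prompts on the BPI?**

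- No forcing: rules out insistence, but not suggestion.
- No guessing: governs what the assessor enters as a correction, not what the assessor says to the participant.
- Change only when certain of a data-entry error: applies to a completed assessment, whereas the prompting takes place during it.
- System stop: requires a flagged answer to be resolved before the interview goes on. The documents do not say which BPI entries, if any, are flagged.

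So the limits reduce the risk but do not remove it.

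**2. What does prompting do to the between-arm comparison?** Section 8.1 regresses change on arm indicators. If prompting shifts mean change by the same amount *b* in every arm, the contrast is (Δ_active + *b*) − (Δ_placebo + *b*) = Δ_active − Δ_placebo, so there is no bias. The spread of scores may still be altered.

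**3. Could prompting be related to arm?** Staff are to be blinded (sections 2.3, 3.1 and 3.2), doses look identical (3.3), and placebo and active capsules are indistinguishable by look and taste (3.3.C). Two routes remain possible.

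- *Through the trigger.* Under section 6.2, "the RA will ask the participant how he or she feels and review the list of symptoms of concern". The checklist in section 6.3 includes joint or muscle pain, abdominal pain and headaches, which section 3.3.A lists as common with naltrexone, although at 50 mg and expected to be milder at 4.5 mg. If one arm reports such symptoms more often, an evenly applied rule could prompt that arm more.
- *Through a guess at the arm.* Drowsiness, double vision, unusual eye movement and lack of coordination are on the checklist and in the gabapentin list of section 3.3.B. The documents give no usable frequency for them.

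Baseline questions precede randomization (sections 3.2 and 4.4), so arm-related prompting could act only on follow-up ratings.

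**4. How large might it be?** First, the plan's own figure from section 2.7.A, with SD 2.9 and 13 completers per arm (24 df, t = 2.064):

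full 95% CI width = 2 × 2.064 × 2.9 × √(2/13) = 4.70, against the stated maximum of 4.7; half-width 2.35.

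The rest is illustration. Assumptions not in the documents: BPI severity is the mean of four 0–10 items; 10–30% of one arm have 1–2 items moved by 1–3 points, all in one direction; no movement in the comparison arm.

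shift = share × points × items / 4

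- low: 0.10 × 1 × 1 / 4 = 0.025
- middle: 0.20 × 2 × 1 / 4 = 0.10
- high: 0.30 × 3 × 2 / 4 = 0.45, or 0.45 / 2.9 = 0.16 SD

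With no true effect, the chance of a false positive at two-sided 0.025 (noncentral t, 24 df, noncentrality = shift / [2.9 × √(2/13)] = shift / 1.14) rises from 2.5% to 2.8% for a shift of 0.25 and to 3.8% for 0.5, a value just above the top of the range.

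**The case against.** The best defence is that section 4.5 is mild and bounded. It covers only answers that conflict or make no sense, and it leaves the decision with the participant. A clear contradiction, such as least pain rated above worst pain, suggests a misread item, and clarifying it helps validity. That stands, and it is why keeping every answer strictly as first given would be the wrong remedy.

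The defence also says that the text does not call it illogical for pain to disagree with mood or function. That is correct: a reader might infer that assessors are told to reconcile pain with other scales, but no such instruction exists. The wording on conflicts between sections does not exclude it either, and that is the gap.

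A reader might also infer that the rule biases the gabapentin–placebo contrast. The documents do not support this. An inconsistent answer must occur, prompting must be related to arm, it must lean one way, and the participant must go along with it. The side-effect lists for the two drugs overlap, for example in nausea, vomiting, tremor and drowsiness. Dizziness is not evidence of gabapentin here: section 3.3.B lists lack of coordination, section 3.3.A lists dizziness as uncommon with naltrexone, and the checklist merges the two.

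Finally, the form specifications and training content are not in the documents and may already deal with this.

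**Conclusion.** The point holds as a gap in how the primary outcome is elicited. Prompting toward logical answers is a stated rule, the BPI is within its reach, and the limits do not prevent leading before completion. The likely consequence is added noise or a shift common to all arms. Bias between arms is a possibility, not a finding.

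Its size cannot be derived from the documents. Even the top of the assumed range is about a fifth of the planned half-width (0.45 / 2.35 = 0.19), and it needs about 4 of 13 participants in one arm (0.30 × 13 = 3.9) to be moved substantially in the same direction. The four-item scoring behind it is also assumed, since section 5.1 refers only to a modified short form. The case for change rests on the low cost of protecting a self-rated primary outcome, not on a demonstrated distortion. Label: cheap improvement.

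**What to change.** Amend section 4.5 as follows.

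- Limit prompting toward more logical answers to factual items: dates, medications, the drinking calendar and demographics.
- For BPI items and other self-rated scales, allow only a neutral, word-for-word re-read of the item, and only when the value is missing, out of range, or impossible within the same scale (for example, least pain above worst pain). Never prompt because the rating disagrees with another section.
- Let the participant decide, and record both the first and the final answer.
- Make any REDCap hard stop on these items accept an answer that the participant confirms.

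The cost is a short text change, a training note and a REDCap setting. The downside is that a few inconsistent ratings will stay in the data. Because both answers are kept, their number by arm can be reported, and the primary model can be rerun on first answers as a check.
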